#### ***8.4.3 Reporting of Pregnancy***

Reporting of pregnancy will be to the treating physician, PI, NYSPI IRB and DSMP. There is no ability to remove a Vivitrol injection from a pregnant participant. Although it is not desirable to maintain a pregnant participant in a PK study as hormonal changes due to pregnancy may adversely affect the PK of the IP, as Vivitrol is currently an approved medication, there are no major concerns for the participant's safety if they become pregnant. However pregnant participants will have their data after confirmed pregnancy analyzed separately in case there are changes in PK characteristics as a result of the pregnancy. Any pregnancies will also be reported to the FDA in annual progress reports.

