### 5.2 PARTICIPANT EXCLUSION CRITERIA

Participants will not be eligible for the study if they meet any of the following criteria:

- Is currently on active NTX medication.
- Positive UDS at screening for illicit substances.
- Has a condition which requires treatment with opioid based medication.
- Has a known hypersensitivity to NTX.
- Is prone to skin rashes, irritation or has a skin condition such as recurrent eczema that is likely to impact the injection site area, or as determined by the evaluating physician.
- Demonstrates any abnormal skin tissue in the proposed injection area.
- Is pregnant or planning to be. Women need to have negative pregnancy test at screening. Women need to agree to practice an effective method of contraception throughout participation.
- Participant is breastfeeding or planning to be.
- Has a current significant neurological (including cognitive and psychiatric disorders),
- Any clinically important abnormal finding as determined by medical history, physical examination, ECG or clinical laboratory tests.
- Any additional condition(s) that in the investigator's opinion would prohibit the participant from completing the study or would not be in the best interest

of the participant.

- ALT or AST >3 times the upper end of the laboratory normal range.
- Any methadone use 14 days prior to screening, and up to Study Day 0.
- Current DSM 5 diagnosis of schizophrenia, bipolar, anxiety, or depressive disorder, confirmed by MINI assessment, or currently treated with medications for anxiety or depression. Past history (in remission DSM 5 classification) of anxiety or depression is not exclusionary.
- Any elevated risk for suicide measured using the Columbia Suicide Severity Rating Scale, endorsing any of the items in the past month (C-SSRS, Lifetime)
- Is participating or intending to participate in any other clinical trial during the duration of this study.
- Is allergic to any of the ingredients in Vivitrol or the diluent used to mix Vivitrol (i.e. carboxymethylcellulose sodium, polysorbate 20, sodium chloride, sodium hydroxide and hydrochloric acid as pH adjusters, in water for injection).

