## 5.4 PARTICIPANT WITHDRAWAL OR TERMINATION

### 5.4.1 *Reasons for Withdrawal or Termination*

- A participant may withdraw from the study at any time or for any reason without being obliged to divulge their reason for doing so to the investigators or clinic staff.
- A participant may be withdrawn from the study if there are unacceptable AEs, laboratory abnormalities or any other medical condition or situation including distress due to effects of any study procedure or medication.
- A participant may be withdrawn from the study if in the opinion of the treating clinician the participant's interests are best served by withdrawing from the study.
- A participant may be withdrawn from the study if the participant meets an exclusion criterion (either newly developed or not previously recognized) that precludes further study participation.

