### 5.4.2 *Handling of Participant Withdrawals or Termination*

Participants, who do not receive the IP (i.e. Vivitrol), for any reason, are not considered study failures. A participant may be discontinued from the study at any time if the participant, investigator, or Sponsor determines that it is not in the best interest of the participant to continue participation. Reasons for discontinuation may include:

- Adverse event
- Withdrawal of participant
- Lost to follow-up
- Study terminated by investigator
- Pregnancy
- Clinical worsening
- Other

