#### 5.4.2.1 Participant Monitoring and Removal from Study

The psychiatrist and/or therapist will assess appropriateness for continuation in the research study on a continuous basis and will remove from the trial participants with significant clinical deterioration or noncompliance of a type which could be dangerous. Criteria for removal from the study will include:

1. Clinical deterioration which cannot be managed safely in the context of outpatient treatment. This would include a participant who becomes suicidal, or a participant who goes on drug binges (including non-opiate drugs).
2. Elevation of liver enzymes  $>3$  times normal. The PI or a study physician is available 24 hours/day by phone in case of emergency.

For those who withdraw from the study may request to withdraw from data collection and have no further contact with study site. Participants shall be informed that for a period of time 30 days after their last Vivitrol injection there may a risk that opioid based medication may have a reduced affect. There is no option to remove Vivitrol from a participant.

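### Nothing in the protocol makes a confirmed pregnancy stop dosing, or has the scheduled pregnancy test read before injections 2 to 6

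*Combined protocol and SAP*

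**What the plan says.** **Entry.** Section 5.2 excludes pregnant women. It adds "Women need to have negative pregnancy test at screening" and "Women need to agree to practice an effective method of contraception throughout participation".

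**After entry.** Section 5.4.1 says "A participant may be withdrawn from the study if the participant meets an exclusion criterion", where that criterion rules out further participation. Section 5.4.2 lists pregnancy under the words "Reasons for discontinuation may include". Section 5.4.2.1 is firmer: study clinicians "will remove from the trial participants with significant clinical deterioration or noncompliance of a type which could be dangerous". The two removal criteria listed there are clinical deterioration and liver enzymes above three times normal.

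**Pregnancy section.** Section 8.4.3 routes every pregnancy to the treating physician, the principal investigator, the IRB and the safety monitoring panel. It states "There is no ability to remove a Vivitrol injection from a pregnant participant". It discourages retention on PK grounds ("it is not desirable to maintain a pregnant participant in a PK study as hormonal changes due to pregnancy may adversely affect the PK"), then sees no major safety concern because the product is approved. It adds that "pregnant participants will have their data after confirmed pregnancy analyzed separately".

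**Testing.** Sections 7.3.3.4 and 7.3.3.5 schedule a pregnancy test, where applicable, at the visits for injections 2 to 6. Section 7.2.1 has a positive urine result confirmed by blood. Section 6.1.7, on dose modifications and delays, is marked as not applicable.

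**The concern.** Each route from a confirmed pregnancy to stopping the drug is permissive, and the one mandatory removal provision does not name pregnancy. A clinician who turns to 8.4.3 finds a preference against retention based on PK, followed by reassurance on safety and a plan for the later data. Two careful clinicians could decide differently about the next injection.

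The test itself carries no stated consequence. If it is read after the injection, or if the blood confirmation comes back later, the dose has already been given and cannot be withdrawn.

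What is at stake is an irreversible exposure in a healthy volunteer for whom section 2.3.2 states no known benefit. Nor does the trial gain much from it, because data after confirmed pregnancy are analysed separately.

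**Working it through.** **Step 1: reproduce the schedule.** Section 4.1 and Table 7-1 footnote 7 give six injections, 28 days apart from Day 0. Dose *k* falls on Day 28 × (*k* − 1), which gives Days 0, 28, 56, 84, 112 and 140. That is six doses, as stated.

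**Step 2: doses still to come.** If pregnancy is found at the visit for dose *k*, before that injection, the doses remaining are 6 − (*k* − 1) = 7 − *k*.

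| Found before the injection on | Dose due | Doses remaining |
|---|---|---|
| Day 28 | 2 | 7 − 2 = 5 |
| Day 56 | 3 | 7 − 3 = 4 |
| Day 84 | 4 | 7 − 4 = 3 |
| Day 112 | 5 | 7 − 5 = 2 |
| Day 140 | 6 | 7 − 6 = 1 |
| After the Day 140 injection | none | 0 |

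These are counts of scheduled doses and not a risk estimate. The documents give neither the number of women nor a pregnancy rate.

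**Step 3: does any provision turn a confirmed pregnancy into a stop?**

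| Section | Bearing on pregnancy | Binding? |
|---|---|---|
| 5.2 | Exclusion; negative test at screening | Yes, at entry only |
| 5.4.1 | Newly met exclusion criterion | No, permissive |
| 5.4.2 | Pregnancy listed as a reason | No, permissive |
| 5.4.2.1 | Pregnancy not listed | Binding, but for other events |
| 8.4.3 | Retention discouraged; reporting; separate analysis | No stop stated |

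**Step 4: does the test gate the injection?** For Days 28 to 112, section 7.3.3.5 places the safety bloods and the trough sample just before re-dosing. Section 7.3.3.4 likewise places the Day 140 PK sample before the injection. In both, the pregnancy test is mentioned separately, with no order and no required result. Section 7.2.1 does not say whether that day's injection waits for the confirmatory blood test. By contrast, the naloxone challenge is written as a gate: the study schematic and section 7.1.1.3 require a pass before dosing.

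**Step 5: timing if a dose is held.** The dosing window is not consistent. The heading of 7.3.3.5 and the matching Table 7-1 row give ±1 day, while footnote 7 gives ±2 days for the injection. The Day 140 pre-dose PK sample is ±1 day (7.3.3.4 and footnote 5). Section 3.1 defines the trough as the level 28 days after each dose. A dose held from Day 28 to Day 30, with the next trough still drawn on Day 56, gives 56 − 30 = 26 days. Held to Day 29, it gives 56 − 29 = 27 days.

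**The case against.** The best defence is that the plan already leans towards stopping. Contraception is required throughout. Pregnancy is a named discontinuation reason, and a newly met exclusion criterion is a further ground. The permissive wording is the house style of these lists (unacceptable adverse events are worded the same way), so it does not signal leniency about pregnancy in particular. The decision is not one clinician's alone: each pregnancy goes to the principal investigator, the IRB and the safety monitoring panel, and section 5.4.2.1 has fitness to continue assessed continuously. Section 7.3.3.1 also lists a pregnancy test on Day 0 ahead of the naloxone challenge and the first injection. With at most 15 participants, the situation may never arise.

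All of that stands, and it keeps the point modest. It does not close the gap. Permission to stop is not a rule to stop, reporting does not by itself hold the dose due that day, and the Day 0 test covers only the first injection.

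The practical objection to a test-before-dose rule also stands in part. Section 7.2.1 describes samples going to an outside laboratory, and nothing says the urine pregnancy test is read on site. If it is not, the rule would affect every woman at five visits, not only those with a false positive. Turnaround of the confirmatory blood test is not given either.

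A reader might infer that the protocol directs continued dosing in pregnancy, or that its statement of no major safety concern is wrong. Neither is supported. No text instructs anyone to continue, and nothing in the documents shows that statement to be false.

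**Conclusion.** The point holds as a cheap improvement for participant safety. On the available text, a confirmed pregnancy does not stop dosing by rule, and the scheduled test need not be read before injections 2 to 6. Between 1 and 5 remaining doses therefore rest on judgement, depending on when pregnancy is found, and none if it is found after the sixth.

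This rests on the protocol as published. Consent pages are not part of it, and a rule could sit there. The likelihood of the event is low and cannot be quantified from the documents.

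It would be wrong to read this as a threat to the primary PK results, since section 8.4.3 keeps data after confirmed pregnancy apart. It would also be wrong to say that testing is missing, since tests are scheduled. What is missing is the consequence of the result.

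**What to change.** 1. **Section 8.4.3.** Add: *Confirmed pregnancy stops all further Vivitrol injections; the participant stays in PK and safety follow-up for doses already given, and data after confirmed pregnancy are analysed separately.* A stop-dosing rule is preferable to a removal criterion because it keeps follow-up of drug that cannot be taken out.
2. **Sections 7.3.3.4 and 7.3.3.5.** State that, for women of childbearing potential, the scheduled urine test is read before the injection. If it is positive, take the scheduled trough sample and withhold the injection until the blood test is negative, within the protocol's dosing window. First reconcile the ±1 day and ±2 day windows, and confirm that the urine test can be read on site.
3. **Section 6.1.7.** Cross-reference this hold.

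**Cost.** The tests are already scheduled, so this is mainly a change of text. A false-positive or slow result may delay a dose or cause that woman to miss it. A delayed dose shortens the interval to the next trough unless later visits are timed from the actual dose, so the text should say which applies. A woman stopped before Day 140 gives no sixth-dose profile, but under 8.4.3 that profile would have been outside the main summaries anyway. Section 5.3.1 already allows for 15 − 12 = 3 non-completers.

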### **8.5 STUDY HALTING RULES**

#### ***8.5.1 Study Termination***

The Sponsor reserves the right to close the investigational sites or terminate the study at any time. The PI may initiate site closure at any time, provided there is reasonable cause and sufficient notice is given in advance of the intended termination. Reasons for the early closure of an investigational site by the Sponsor or PI, or termination of a study by the Sponsor, may include but are not limited to:

- failure of the PI to comply with the protocol, the Sponsor's procedures, or with GCP guidelines
- safety concerns
- inadequate recruitment of participants by the PI

Study termination will be reported to the PI, NYSPI IRB, DSMP and FDA.

#### ***8.5.2 On-Site Audits***

Representatives of the Sponsor's quality assurance department may visit the site to carry out

an audit of the study in compliance with regulatory guidelines and the Sponsor's standard operating procedures. Audits and clinical trial monitoring will also be carried out by the CRO, Clinilabs, during the trial period. These audits will require access to all study records, including source documents, for inspection and comparison with the CRFs. Participant privacy must, however, be respected. Similar auditing procedures may also be conducted by agents of any regulatory body reviewing the results of this study in support of a regulatory submission. The PI should immediately notify the Sponsor if they have been contacted by a regulatory agency concerning an upcoming inspection.

## 8.6 DATA AND SAFETY MONITORING PLAN ADMINISTRATION

### 8.6.1 *Responsibility for data and safety monitoring (DSM)*

The study PI, [name], is required to be present for all DSMB meetings to provide reports for all accumulated data from the trial. The PI will also be primarily responsible for the implementation of any recommendations from the DSMB. The PI will be assisted in this duty by [name], study Medical Monitor.

### 8.6.2 *Frequency of DSM*

Ongoing data and safety monitoring will be conducted weekly during research team meetings of the PI with the investigative team. Every three months, the PI and the medical monitor will review the number of participants enrolled, the number who completed the protocol, the number who dropped out of the protocol prior to completion (and reason why), any AEs, procedures for assuring participants privacy and confidentiality, and the quality and integrity of the data collected. Corrective action will be taken if needed. IRB study protocols and informed consent documents will be reviewed annually by the IRB. Reports of enrollment and retention and reporting of AEs are required with these renewals.

In addition, all studies involving human participants are periodically and systematically reviewed by the New York State Quality Assurance Staff. These procedures assure protocol compliance by conducting unannounced reviews of participants' research charts, comparing research charts to the IRB protocol. All SAEs will be reported to the FDA (as appropriate) and the DSMB in a timely fashion.

A separate DSMB (see section 8.6.3 for details) will meet quarterly and the *PI and study monitor will evaluate SAEs and bring them to the attention of the DSMB at the next scheduled meeting or sooner if there are significant concerns*. Ad hoc meetings may also occur if any study related issues arise during the course of the study.

### 8.6.3 *DSMB Plan*

The DSMB will be chaired by [name], a Professor of Psychiatry at New York University and a senior addiction pharmacotherapy researcher. Two additional faculty members from the division will join the DSMB; [name], an opioid dependence treatment investigator in the division, and [name], another research psychiatrist in the division. In addition, two research physicians from outside of the division will join the DSMB, [name], a senior investigator in the Department of Psychiatry at Columbia University and expert in mood disorder pharmacotherapy, and [name], an infection disease specialist at Yale School of Medicine, who has extensive experience studying naltrexone use in treatment for patients with hepatitis and HIV.

The DSMB will meet before the study launch and quarterly to conduct initial and ongoing study review and review all AEs that occurred in the study. PI and study monitor will evaluate SAEs and bring them to the attention of the DSMB at the next scheduled meeting or sooner if there are significant concerns. For each SAE, the PI and covering physician will present a synopsis of how it occurred and how the incident was handled clinically so that DSMB can assess how the event was managed and if there are any recommendations that will maintain the high quality of care provided to research participants. Ad hoc meetings may also occur as needed to address study related issues.

All DSMB members will be asked to submit in writing any potential conflict of interest pertaining to the study. The DSMB will prepare a report in response to any SAE review meetings and will submit a DSM report annually. Reports will be submitted to the Sponsor and other authorities as appropriate. This report will include the following:

- a) Brief description of the trial,
- b) Baseline socio-demographic characteristics,
- c) Retention and disposition of study participants,
- d) Quality assurance issues,
- e) Regulatory issues,
- f) AEs,
- g) SAEs
- h) Efficacy

## **9 CLINICAL MONITORING**

This study may be subject to audit or inspection by representatives from the NYSPI IRB, DSMB or FDA.

Data from this study will be monitored by staff from the CRO, Clinilabs, for compliance with GCP principals. Monitoring will include review of CRFs and other study documents for protocol compliance, data accuracy and completeness. Monitoring will include review of the investigator's site file and drug handling records. Clinilabs will be given direct access to source documents, CRFs and other study-related documents. By signing the informed consent form, the participant authorizes Clinilabs staff direct access to their medical records and the study data.

## 10 STATISTICAL CONSIDERATIONS

### 10.1 STATISTICAL AND ANALYTICAL PLANS

NTX (and 6 $\beta$ N) plasma concentration data will be explored by Non-Compartmental Analysis (NCA). Mean, median, standard deviation and coefficient of variation of parameters such as AUC0-28days, Ctrough, and Cmax will be reported for each day for which the parameter is available, which is the primary objective of this study. The Accumulation Ratio (AR) of these parameters comparing the sixth with the first administration will inform us if there is accumulation of NTX (and 6 $\beta$ N) and if this accumulation is substantial. This is a secondary objective of this study.

Comparison of the cumulative AUC0-28days, as well as overall Cmax and Ctrough during six consecutive Vivitrol administrations with previously determined 6-month data after OLANI (as determined in study GM0017) will inform us about bioequivalence of the two formulations. This is an exploratory objective of this study. Appropriate paired statistics will be used to compare the first with the sixth Vivitrol administration and to compare 6 months of Vivitrol with six months of OLANI.

### 10.2 STATISTICAL HYPOTHESES

N/A

### 10.3 ANALYSIS DATASETS

The analysis will be performed based on Intention-to-Treat and Per-Protocol in all participants enrolled. Assessment of primary outcomes will be performed on participants who complete at least 75% of applicable time points.

### 10.4 DESCRIPTION OF STATISTICAL METHODS

#### 10.4.1 General Approach

Pharmacokinetic parameters will be assessed from the NTX and 6 $\beta$ N plasma data using PK software (Phoenix Winnonlin, Princeton, NJ) and expressed and tabulated as a mean, median, standard deviation and co-efficient of variation for each administration of Vivitrol.

Participants who submitted at least 75% valid pharmacokinetic blood samples from all study arms shall be measured for pharmacokinetic parameters of Cmax, Ctrough, Tmax, AUC0-28days and AUC0- $\infty$ .

Accumulation of NTX and its metabolite is investigated using the Accumulation Ratio (AR) for AUC0-28days, AUC0- $\infty$ , Cmax and Ctrough. An accumulation ratio of 1 (e.g., AUC0-28days, 6th administration / AUC0-28days, 1st administration) indicates that there is no accumulation.

As an exploratory endpoint we will also compare the cumulative AUC0-28days during 6 consecutive administrations of Vivitrol with the AUC0-6months after OLANI, which was determined for each of these patients in study GM0017. In addition, Cmax and Ctrough will be compared for both formulations. Comparisons will be done using the ratio of the geometric mean of these parameters for each formulation.

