#### ***10.4.3 Analysis of the Secondary Endpoint(s)***

We will calculate the Accumulation Ratio (AR) for  $AUC_{0-28days}$ ,  $C_{max}$  and  $C_{trough}$  by comparing the parameter after one administration with the same parameter after another, e.g.,  $AUC_{0-28days, 6th administration} / AUC_{0-28days, 1st administration}$ . An AR of 1 (or a value close to 1) indicates little to no accumulation.

This analysis will be accompanied by visual inspection of the plasma concentration time curves of NTX and its metabolite, which will be plotted graphically. The visual inspections and comparisons of the curves are exploratory endpoints of this study.

Visual inspection of the curves will also inform us if the plasma concentration time profile after the first administration is similar to that after the sixth administration of Vivitrol.

Visual inspection of the Vivitrol curves and comparison with the visual inspection of the OLANI (as determined in GM0017) curves in the same patients might also inform us if earlier identified rapid metabolizers of the OLANI formulation are also rapid metabolizers of the Vivitrol formulation.

Use of opioids, cocaine, marijuana, and alcohol for each day of the study will be determined based on results of urine toxicology and self-report. Proportion of days with substance use for each participant will be summarized.

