#### ***10.4.12 Exploratory Analyses***

No exploratory analysis will be conducted.

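### The exploratory Vivitrol–OLANI comparison is said to inform about bioequivalence, but its only named statistic is a ratio without an interval, the sequence is fixed, and 10.4.12 contradicts the plan to run it

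*Combined protocol and SAP*

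**What the plan says.** Section 10.1 plans to compare cumulative AUC, overall Cmax and Ctrough across six Vivitrol administrations with the six-month OLANI data from GM 0017. It says that this "will inform us about bioequivalence of the two formulations. This is an exploratory objective of this study". On method, the same section says "Appropriate paired statistics will be used to compare the first with the sixth Vivitrol administration" and, later in that sentence, "to compare 6 months of Vivitrol with six months of OLANI". It names no test, scale or interval.

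Section 10.4.1 takes up the comparison again ("As an exploratory endpoint we will also compare the cumulative") and gives the one statistic that the plan names: "Comparisons will be done using the ratio of the geometric mean of these parameters for each formulation". Section 10.4.3 adds visual comparison of the curves, including Vivitrol against OLANI, and states: "The visual inspections and comparisons of the curves are exploratory endpoints of this study".

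Section 10.2 (hypotheses) is marked not applicable. Section 10.4.12 says: "No exploratory analysis will be conducted".

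**The concern.** There are three separate problems.

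- **No measure of uncertainty.** Bioequivalence is a statement about how far the true ratio could lie from 1. A ratio of geometric means alone does not address that. Confidence intervals are planned for adherence (10.4.6) and baseline characteristics (10.4.7), but not for this comparison.
- **Fixed sequence.** Sections 4.1 and 5.1 admit only people who have already received OLANI in GM 0017. Any difference between products is mixed with differences of period and study, and an interval does not remove that.
- **Contradiction.** Three sections plan exploratory work, and 10.4.12 says there will be none.

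Section 2.2 gives comparison with OLANI as the reason for recruiting only GM 0017 participants, and says Vivitrol is to be the approved comparator in an OLANI application. A ratio near 1 from about 12 people could therefore be reported under a bioequivalence label without its uncertainty, and the paired method could be chosen after the data are seen.

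**Working it through.** **The plan's own figure.** The only sample-size arithmetic is in 5.3.1: 12 of 15 expected to complete, and 12/15 = 0.80, which agrees with the stated 80%. No precision or power figure exists for the OLANI comparison, so there is nothing further to reproduce.

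**Inputs.** Pairs: n = 12 (5.3.1 and 10.5). Observed ratio: set to 1.00 for illustration. The within-participant CV, the 90% level and the 0.80–1.25 limits are my assumptions; none is in the documents. The formula also assumes the same within-participant variance for the implant and the injection.

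**Formulas.** Log-scale within-participant SD: s = √ln(1 + CV²). Half-width of the 90% interval for the mean paired log difference: h = t(0.95, n−1) × s × √(2/n). Limits: exp(−h) and exp(+h).

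For n = 12, t(0.95, 11) = 1.796 and √(2/12) = 0.408, so h = 0.733 × s.

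| Assumed CV | s | h | 90% CI at ratio 1.00 |
|---|---|---|---|
| 20% | 0.198 | 0.145 | 0.86–1.16 |
| 30% | 0.294 | 0.215 | 0.81–1.24 |
| 40% | 0.385 | 0.282 | 0.75–1.33 |
| 50% | 0.472 | 0.346 | 0.71–1.41 |

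The lower limit in the first row is 0.8649 before rounding.

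**Break-even CV.** The interval around 1.00 stays inside 0.80–1.25 when h is below ln 1.25 = 0.223. With 12 pairs this needs s < 0.223/0.733 = 0.304, a CV below about 31%. With all 15 completing, t(0.95, 14) × √(2/15) = 0.643, so s < 0.347, a CV below about 36%.

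**What the sampling supports.** Sections 7.1.1.5 and 7.3.3.5 and the notes to Table 7-1 give intensive sampling after doses 1 and 6 only. Doses 2 to 5 have one pre-dose sample at the end of each interval. So:

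- Ctrough is observed after all six doses (Days 28, 56, 84, 112, 140 and 168).
- AUC over a dosing interval, and Cmax, are observed for doses 1 and 6 only.
- The cumulative six-dose AUC, the lead parameter of the comparison, is not directly observed.

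**The contradiction.** Section 10.1 calls the comparison an exploratory objective, 10.4.1 an exploratory endpoint, and 10.4.3 adds exploratory comparisons of curves. Section 10.4.12 excludes exploratory analysis without exception. These statements cannot all stand.

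**The case against.** The strongest reply is that the plan does not set out to demonstrate bioequivalence. The comparison is labelled exploratory in both places, it is absent from the primary and secondary objectives, and 4.1 refers to a future bioequivalence study. Marking hypotheses as not applicable suits a descriptive PK study. All of this stands, and it limits the weight of the point. It does not justify a bioequivalence label on this study's own comparison when no interval is planned.

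A reader might go further in three ways that the documents do not support:

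- *That a ratio is all that will be computed.* Section 10.1 also promises paired statistics, which could yield an interval. The gap is that the method is unnamed, not that an interval is excluded.
- *That a non-significant paired test will be taken as equivalence.* No section says so, and there is no decision rule. It is a risk of leaving the method open.
- *That 10.4.12 cancels the OLANI comparison.* It is a general line that does not mention OLANI and may be leftover wording. It still conflicts with the specific sections.

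On sequence, the Protocol Summary and 2.2 disclose that OLANI came first and foresee a later group given Vivitrol first. That group is only planned, would receive two Vivitrol doses, and does not remove the confounding here.

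On size, the CVs and limits are assumed, and at 20% and 30% a ratio of 1.00 stays inside the limits. A ratio near 1 is itself hypothetical: 5.1 gives 3.6 g of OLANI against 6 × 380 mg = 2.28 g of Vivitrol. Under the same assumptions, though, the width in relative terms does not depend on the ratio observed. Standard deviations for the Vivitrol parameters (10.1, 10.4.1, 10.4.2) and listings of individual data (10.4.11) help a reader, but neither is an interval for the paired ratio.

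**Conclusion.** The point holds as a fault of specification and wording in an exploratory analysis. The named statistic cannot support the stated purpose, the paired method is undefined, the fixed sequence confounds formulation with period and study, and 10.4.12 contradicts three other sections. The primary and secondary objectives are unaffected.

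The size is illustrative. Under the assumed CVs of 20% to 50%, 12 pairs leave a true ratio uncertain by a factor of about 1.16 to 1.41 either way. At 40% or more, even an observed ratio of exactly 1.00 has an interval outside 0.80–1.25. The need for an interval does not depend on those assumptions. The documents do not support reading the plan as a failed bioequivalence demonstration, since it does not claim to be one.

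**What to change.** Before analysis:

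1. In 10.1 and 10.4.1, replace both the unnamed paired methods for the OLANI comparison and the bare ratio with one stated method. Take the within-participant log ratio of Vivitrol to OLANI, and report it as a geometric mean ratio with a 90% confidence interval from the paired log differences.
2. List the parameters to which this applies, limited to those that the sampling supports for both products. Acknowledge that full AUC is sampled only for doses 1 and 6, so the cumulative six-dose AUC is not directly observed. The GM 0017 schedule is not in these documents, so the sponsor must confirm the OLANI side.
3. In 10.1, replace the bioequivalence wording with a statement that the aim is to estimate relative exposure, exploratory and in a fixed sequence.
4. Rewrite 10.4.12 so that it lists the exploratory analyses already planned in 10.1, 10.4.1 and 10.4.3.

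The cost is a wording amendment and a few lines of analysis code, with no new participants, visits or samples. The downside is a more modest claim.
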